### **SECONDARY OUTCOMES:**

- Describe the effect of PEEP during SBT on the ultrasound lung aeration pattern.
- Describe the effect of aspiration during extubation on the ultrasound lung aeration pattern.
- Describe the effect of the diaphragm (thickness, thickening fraction, and thickness evolution between admission and SBT) on the ultrasound lung aeration pattern.
- Describe the effect of the activity of the respiratory accessory muscles (parasternal thickness and thickening) on the pattern of lung aeration.
- Describe the pattern of ultrasound aeration, diaphragmatic thickness and accessory muscles in patients who fail extubation (1. Does not tolerate SBT and 2. Tolerates SBT and reintubation <72 hours).
- Describe the related variables to ultrasound lung aeration loss.

- Describe influence on aeration pattern of prophylactic HFNC or NIV and physiotherapy.
- Describe the ultrasound variables (lung aeration, diaphragm and accessory muscles) related to extubation failure. (1. Does not tolerate SBT and 2. Tolerates SBT and reintubation <72 hours.
- Describe and assess significant differences in the degree of ultrasound derecruitment (recruitment or  $\Delta$ RCT) in each strategy (standard and preservation of pulmonary volume)
- Describe and assess significant differences in ultrasound derecruitment ( $\Delta$ RCT) in patients who pass and those who do not pass SBT.
- Assess ultrasound de-recruitment ( $\Delta$ RCT) and correlate to ICU stay, hospital stay, extubation failure and mortality.

#### EXPLORATORY OUTCOMES:

- Specifically assess changes in lung aeration in posterobasal regions.
- Describe the relationship between Maximal Inspiratory Pressure, P0.1 and Pocc and diaphragmatic thickness.

## METHODS

### STUDY DESIGN AND PROTOCOL

Nested substudy in the blinded randomized controlled prospective multicenter clinical trial: “Preserving lung volume at extubation. A prospective, randomized controlled multicenter trial” (NCT05526053) (CEI 22/67)

### INCLUSION CRITERIA FOR PARTICIPATING CENTERS

Before starting the study, a technical and competence evaluation of the centres participating in the ultrasound substudy will be carried out (at least 15 have shown interest) within the 34 participating centres in the RCT *Preserving lung volume at Extubation*. At least one collaborator will be designated in charge of the centre with accredited experience in lung ultrasound according to the recommendations of the APECHO study (xx) through a course endorsed by the scientific society of intensive care or ultrasound, or at least 25 complete examinations supervised by an expert, who will supervise the personnel of their competent unit for the acquisition of the quality ultrasound images.

Availability of suitable convex and linear probes with the ability to record 3 to 10 seconds video clips.

Ability to download ultrasound images in DICOM format.

Passing the trial period of sending at least 5 scans (all LUSm windows, diaphragmatic and intercostal thickening of 5 different patients) to test that meet the described requirements and can be technically correctly interpreted by an independent observer.

#### PATIENT INCLUSION CRITERIA

Patients over 18 years with at least 24h of mechanical ventilation and criteria for performing a SBT (Table 1) who participate in the study “Preserving lung volume at extubation. A multicenter prospective, randomized controlled clinical trial (RCT)” (NCT05526053) and agree to participate and sign the specific informed consent (IC) for this study.

Table 1. SBT criteria.

- |  |
|--|
| 

- Effective cough: ability to mobilize secretions up to the endotracheal tube.

- Absence of excessive secretions: <3 aspirations in the last 8 hours.

- Hemodynamic stability: HR<140, SBP 90-160mmHg, no vasopressors or low doses.

- Resolution or improvement of the cause of intubation.

- Adequate oxygenation: SpO2>90% with FiO2<0,4.

- Correct ventilatory mechanics: RR<35rpm, MIP < -20cmH2O, TV >5 and <10ml/kg, RR/TV index <100 bpm/L.

- Adequate level of consciousness: GCS>13

 |
|--|

#### EXCLUSION CRITERIA

Tracheostomy, absence of ultrasound window, pulmonary emphysema, pulmonary bullae or pneumothorax that make ultrasound assessment impossible, previous neuromuscular disease or evidence of paralysis or paradoxical diaphragmatic movement during admission, suboptimal image assessment by the operator, absence of personnel specifically endorsed for the acquisition of ultrasound images in the extubation process.

#### SAMPLE SIZE

[figure not shown]
Considering significant a minimum difference of 1 point (SD 2,96) in the LUSm described by Tenza  (from 0 to 24 points) with an alpha error of 5 % and a power of 80 % 186 patients, 93 in each study group are required.

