## **OUTCOMES**

### **PRIMARY OUTCOME:**

Determine the difference in ultrasound lung aeration in two opposing weaning strategies (standard versus lung volume preservation strategy).

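### Ultrasound substudy: 93 patients per group give about 63% power on the plan's own inputs, not 80%; those inputs need 138 to 139 per group

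*Combined protocol and SAP*

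**What the plan says.** The substudy's Sample size section gives its calculation in one sentence. The effect and spread are "Considering significant a minimum difference of 1 point (SD 2,96) in the LUSm", a scale that runs from 0 to 24. The error rates and result follow: "with an alpha error of 5 % and a power of 80 % 186 patients, 93 in each study group are required". Both the 1-point difference and the SD are tied to a cited study of the same score.

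The sentence names no test, sidedness, time point, baseline correlation or allowance for unusable scans. The primary outcome is worded without direction: "Determine the difference in ultrasound lung aeration in two opposing weaning strategies". Under Image acquisition moments, two LUSm scans are essential: one before the spontaneous breathing test (SBT), and one after it. The second is taken immediately after extubation if the SBT succeeds. If it fails, the scan is taken as early as possible, before or just after reconnection to the ventilator.

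**The concern.** A difference, an SD, an alpha, a power and two equal groups fix the sample size for a comparison of two means, so the stated 93 can be checked directly. The standardised effect is 1/2.96 = 0.338, and 93 per group is too few for 80% power at an effect that small.

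The substudy has its own hypothesis, primary outcome and formal sample size. If the real power for the smallest difference it sets out to detect is well below 80%, a non-significant result says much less than the plan implies. A reader who trusts the stated power could take such a result as fair evidence that the lung-volume strategy does not change aeration.

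**Working it through.** **Inputs** (substudy, Sample size, unless noted)

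- Difference δ = 1 LUSm point; SD σ = 2.96.
- Alpha 5%; power 80%; allocation 1:1.
- Sidedness is not stated. Two-sided is assumed because the primary outcome is non-directional; one-sided is also checked.
- The base case is an unadjusted comparison of two independent groups, because no correlation or covariate is stated.

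**Step 1. Try to reproduce 93 per group**

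n per group = 2 (z₁₋α/₂ + z₁₋β)² σ² / δ²

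- Two-sided: 2 × (1.960 + 0.842)² × 2.96² / 1² = 137.5, so 138. The t-test gives 138.5, so 139.
- One-sided: 2 × (1.645 + 0.842)² × 2.96² / 1² = 108.3, so 109. The t-test gives 109.02, so 110.

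Neither gives 93. Against the two-sided figure the shortfall is 1 − 93/138.5 = 33%.

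**Step 2. Power at 93 per group**

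Standard error = 2.96 × √(2/93) = 0.434, so δ/SE = 2.304.

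- Two-sided: Φ(2.304 − 1.960) = Φ(0.344) = 63.4%. The t-test gives 63.0%.
- One-sided: Φ(2.304 − 1.645) = Φ(0.659) = 74.5%. The t-test gives 74.2%.

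**Step 3. What would make 93 per group correct (two-sided, 80% power)**

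| Change one input | Normal formula | t-test |
|---|---|---|
| SD instead of 2.96 | 2.43 | 2.42 |
| Difference instead of 1 point | 1.216 | 1.222 |
| Baseline correlation r in ANCOVA, r = √(1 − 93/n) | 0.569 (n = 137.5) | 0.573 (n = 138.5) |

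None of these values appears in the readable text. If 2.96 is a single-scan SD and a change score is analysed, the correlation needed is 1 − 93/(2 × 137.5) = 0.66, also unstated.

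**Step 4. Other readings tried**

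- A paired (one-sample) formula gives 71 patients in total, which is neither 93 nor 186.
- A rank test raises the number: 137.5/0.955 = 144 per group, or 137.5/0.864 = 159.
- Any allowance for lost scans also raises it.
- For 90% power the same inputs need 185 per group by the normal formula, or 186 by the t-test (185.1 rounded up). The plan's total is 186, so a per-group figure for 90% power may have been read as a total. The documents do not show this, and the finding does not depend on it.

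**Step 5. Power at 93 per group with baseline adjustment**

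Residual SD = 2.96 × √(1 − r²); two-sided t-test.

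| Correlation r | 0.2 | 0.3 | 0.4 | 0.5 | 0.58 | 0.7 |
|---|---|---|---|---|---|---|
| Power | 65% | 67% | 71% | 75% | 80% | 89% |

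**The case against.** The strongest reply is that the calculation may not be fully visible. A figure in the Sample size section is missing from the text reviewed and could hold further inputs. The test is not named, and it cannot be told from the plan whether 2.96 is the SD of a single scan or of something else. With two scans per patient and derecruitment by strategy among the secondary outcomes, an adjusted analysis may have been in mind. The 63% would then understate the power. This stands as a condition on the 63%, which applies to an unadjusted comparison with SD 2.96. It does not rescue the 93: the sentence reads as a complete calculation, its inputs do not give its result, and any correlation relied on needs to be stated with them.

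A second reply is that this is a nested imaging substudy, and the main trial's 822 per group is untouched. That is true and limits the reach of the error. The figure is still the formal justification for the substudy's own primary outcome.

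A third reply concerns the remedy. Baseline adjustment restores 80% only at a correlation the plan does not support, and at r = 0.4 power is 71%. The second scan is also not a single kind of measurement, since its timing depends on whether the SBT succeeded. Some scans may be unusable: the case report form records whether ultrasound was feasible. These points stand, and the fix takes them as conditions.

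**Conclusion.** The concern holds. On the readable inputs, 93 per group gives about 63% power for a 1-point difference, not 80%, and 80% power needs 138 to 139 per group. The chance of missing a true 1-point difference is about 37% rather than 20%. The difference detectable with 80% power at 93 per group is about 1.22 points.

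These figures assume a two-sided, unadjusted comparison of two independent means with SD 2.96 and no lost scans. That the stated number is wrong does not depend on sidedness, because a one-sided test also fails (109 to 110 per group; about 74% power at 93). Losses among the 186 would lower the power further. A baseline-adjusted analysis could justify 93 per group, but only with a correlation of about 0.57 or more, which the plan does not state.

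**What to change.** 1. **Correct the statement.** In the substudy's Sample size section, say that 186 patients (93 per group) give about 63% power for 1 point at SD 2.96 and two-sided 5%, or 80% power for about 1.22 points. State the test and sidedness. If the missing figure or the original calculation used another input, put it in the text.

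2. **Name the primary analysis.** A suitable choice is ANCOVA of the second-scan LUSm by arm, adjusted for the pre-SBT LUSm. State the pre/post correlation assumed and its source, and give the power over a range such as r = 0.3 to 0.7 (67% to 89%). Say how second scans after a failed SBT enter the analysis and how missing or unusable scans are handled.

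3. **If a correlation of about 0.57 cannot be supported,** either keep 186 patients and report the lower power, or raise the target to about 278 (139 per group) plus an allowance for unusable scans.

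Item 1 costs only wording, and a less favourable power figure. Item 2 uses scans already planned, so it needs no new scans or patients, but it does fix a primary analysis that the plan now leaves open. Raising the target in item 3 adds about 92 patients (278 − 186). The main trial plans 2 × 822 = 1,644 patients, and at least 15 of its 34 centres have shown interest in the substudy, so the larger number is not obviously out of reach.

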## STUDY PROCEDURE

### IMAGE ACQUISITION MOMENTS

Images of the LUSm, diaphragm and intercostal musculature windows will be acquired following the scheme [figure 7], regardless of the standard or volume preservation arm.

Figure 7. Scheme of scan moments.

Essential scans:

1: pre-SBT LUSm

2: according to:

- If SBT fail: LUSm as early as possible, whether it can be before reconnection to ventilation or immediately after reconnection (to be specified).

- If SBT success: immediate post-extubation LUSm.

In case of failed SBT or failed extubation, patients do not re-enter the study.

It is recorded if rest has been performed after SBT, prophylactic high-flow oxygen therapy or non-invasive ventilation and respiratory physiotherapy have been indicated.

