## METHODS

Study design and protocol (informed consent in Appendix 1):

Prospective multicenter, controlled, randomized study.

Inclusion criteria: Patients > 18 years who meet weaning criteria (see below) after at least 24 hours of MV, and with informed consent signed by them or their next of kind.

Exclusion criteria: tracheostomy, do-not-reintubate orders, decision of the responsible physician (e.g., due to a preference for a particular weaning technique according to the underlying pathology), absence of informed consent, mental incapacity without legal representation.

Weaning criteria:

- Suitable cough (Ability to raise secretions to the endotracheal tube) (or  $PiMax > -15$  cmH2O).
- Absence of excessive secretions (<3 aspirations in the last 8 hours).
- Resolution or improvement of the pathology that led to intubation.
- Clinical stability (HR <140 bpm, SBP 90-160, without vasopressors or at minimum doses).
- Adequate oxygenation (SatO2 > 90% with FiO2 <0.4).
- Adequate ventilatory mechanics (RR <35 rpm, MIP <-20 cmH2O, Vt > 5 ml / kg, VC > 10 ml/ kg, RR / VT <100 rpm/l).
- Confident awareness level (Glasgow Coma Scale > 13).

Prior to the SBT, attending physicians will state whether they intend to apply prophylactic post-extubation high flow nasal cannula or non-invasive mechanical ventilation. Patients will be in Fowler position (seated at 45° angle), the tracheal secretions will be suctioned before SBT, and FiO2 will remain at the same level than when receiving MV. A cuff-leak test will be performed by deflating the cuff and looking at the difference between inspired and expired volumes.

Patients will be randomized to two weaning strategies (see statistical analysis for more information):

- Standard: PSV 8 cmH2O, PEEP 0 cmH2O for 30 minutes and, when successful, followed by extubation with continuous suctioning.
- Lung volume preservation: PSV 8 cmH2O, PEEP 5 cmH2O for 30 minutes and, when successful, followed by direct extubation without suctioning.

Other components of standard treatment of patients (physiotherapy, nutrition, hydration...) will remain at the discretion of attending physicians and local protocols. During the SBT, if the patient meets any of the criteria for failure (see below), MV will be reconnected with the same parameters as prior to the SBT.

Failure of SBT will be defined as:

- Subjective indexes:

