- Neurological causes: Agitation or anxiety. Low level of consciousness (Glasgow Coma Scale <13).
- Increased respiratory work: use of accessory muscles, facial expression suggesting stress, severe dyspnea.

- Objective indexes:

- Hypoxemia: PaO2 <60 mmHg or SatO2 <90% with FiO2 ≥0.5
- Tachypnea: RR > 35 rpm
- Hemodynamic instability: HR > 140 bpm or >20% from baseline; SBP >180 mmHg or >20% from baseline; SBT <90 mmHg; Cardiac arrhythmias.

Patients who fail the SBT will not be randomized in later SBT tests. The day and time of extubation will be recorded in the CRF.

If the patient successfully passes the SBT, an arterial blood gas analysis may be performed at the end of the test.

It is recommended, but not mandatory, to reconnect the patient to MV to rest for 1 hour and, then, proceed to extubation with or without suctioning as randomized.

Extubation failure at 72 hours (regardless of whether reintubation is required) is defined as:

- Respiratory acidosis, pH <7.32, PaCO2 > 45 mmHg.
- SatO2 <90% or PaO2 <60 mmHg with FiO2 ≥50%.
- Tachypnea > 35 rpm.

- Deterioration of the level of consciousness, Glasgow Coma Scale <13.
- Uncontrollable agitation.
- Clinical signs of muscle fatigue.

In extubation failure patients, the attending physician will decide on the treatment, either support with non-invasive ventilation or with high flow nasal cannula, or reintubation as Standard of Care at the discretion of the attending physician..

Patients who present extubation failure will not be randomized in later SBTs.

During the SBT, interventions that the physician considers necessary to monitor the success of the test, such as echocardiography or thoracic ultrasound, may be performed. In the event that the physician considers that the findings of these tests do not guarantee successful extubation despite fulfillment of extubation criteria according to the study protocol, the attending physician's decision will prevail over the study protocol. In these cases, it will be recorded in the CRF as extubation failure due to "other causes of weaning failure".

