### FACTORS INFLUENCING DURING SBT AND EXTUBATION MANEUVER ON LOSS OF PULMONARY AERATION

- Diaphragm weakness

The diaphragm is the muscle that contributes the most to unassisted ventilation, but the mechanisms why diaphragmatic dysfunction is related to SBT failure remain unclear. They probably involve a combination of a decrease in diaphragm force and an increase in impedance that leads to a loss of lung aeration, alveolar collapse and atelectasis (vii).

- Decreased positive pressure

The decrease in inspiratory positive pressure favours collapse during inspiration, like PEEP withdrawal does during expiration and this increases the work of breathing for alveolar opening. An ongoing RCT (NCT 04939285) compares two strategies with PEEP and no PEEP.

- Secretions aspiration:

Aspiration favours collapse, while the maintenance of PEEP during cuff-deflation and endotracheal tube (ETT) removal according to an RCT (viii) allows the passage of air flow between the ETT and the larynx to improve the discharge of secretions.

[figure not shown]

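### The substudy's test of derecruitment between SBT passers and failers cannot separate SBT failure from the condition in which the second scan is taken

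*Combined protocol and SAP*

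**What the plan says.** The substudy's Secondary Outcomes include a comparison of ultrasound derecruitment (ΔRCT) "in patients who pass and those who do not pass SBT", worded as an assessment of significance and not only as description. Another item correlates ΔRCT with extubation failure, stays and mortality. Two further items divide extubation failure into SBT intolerance and reintubation within 72 hours of a tolerated SBT.

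Image Acquisition Moments lists two essential LUSm scans. The first is before the SBT in everyone. The second depends on the result:

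- Failers: "If SBT fail: LUSm as early as possible, whether it can be before reconnection to ventilation or immediately after reconnection", with the choice to be specified.
- Passers: "If SBT success: immediate post-extubation LUSm".

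The section refers to figure 7 for the scheme. That figure is not shown in the text available.

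The main protocol's Methods set the support around these scans. In the standard arm, PSV 8 with PEEP 0 runs "for 30 minutes and, when successful, followed by extubation with continuous suctioning". In the preservation arm, PSV 8 with PEEP 5 runs "for 30 minutes and, when successful, followed by direct extubation without suctioning". After a failed SBT, "MV will be reconnected with the same parameters as prior to the SBT". For passers, before extubation, "It is recommended, but not mandatory, to reconnect the patient to MV to rest for 1 hour".

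The substudy's CRF section records whether a failer was scanned in SBT mode or after reconnection. Rest after the SBT, prophylactic HFNC or NIV, and physiotherapy are also recorded. The legible text gives no formula for ΔRCT and no rule for handling the difference in scan conditions.

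**The concern.** A change in LUSm from before the SBT to the second scan reflects the patient's response to the SBT and also the pressure and manoeuvres in force at that second scan. The substudy's section on factors influencing loss of aeration says so: "The decrease in inspiratory positive pressure favours collapse during inspiration, like PEEP withdrawal does during expiration". It adds that aspiration of secretions also favours collapse.

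Passers are scanned after the tube and its pressure have been removed, with suctioning in one arm. Failers are scanned while still on SBT support or just after return to their earlier settings. A significant or a null result would therefore be open to two explanations that the data cannot tell apart. The correlation of ΔRCT with extubation failure inherits the problem wherever SBT failers are counted as failures.

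**Working it through.** **Step 1. Second-scan conditions side by side** (substudy Image Acquisition Moments; main protocol Methods)

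| SBT result | Arm | Condition at second essential LUSm |
|---|---|---|
| Pass | Standard | Extubated, with suctioning; possible 1-hour rest on MV beforehand |
| Pass | Preservation | Extubated, no suctioning; possible 1-hour rest on MV beforehand |
| Fail, before reconnection | Standard | PSV 8, PEEP 0 |
| Fail, before reconnection | Preservation | PSV 8, PEEP 5 |
| Fail, after reconnection | Either | Pre-SBT ventilator settings |

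No condition occurs in both a pass row and a fail row, so scan condition is fully aliased with SBT result.

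**Step 2. Do the planned safeguards help?** The CRF item separates the two kinds of failer, but no passer is in either state, so adjustment has no overlap to work with. The reader is blinded to strategy and time of exploration (Image Interpretation). That prevents reader bias but not a real difference in aeration between conditions.

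**Step 3. What the bias can do.** Let d be the true excess loss in failers, and c the extra loss that passers show because of their scan condition. The expected observed difference, failers minus passers, is d − c. With d = 1 point:

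- c = 0.5 gives 0.5 (diluted)
- c = 1 gives 0 (masked)
- c = 2 gives −1 (reversed)
- c = −1 gives 2 (exaggerated)

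The documents give neither d nor c.

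**Step 4. Illustration of false positives when d = 0.** The only sample size in the substudy is 186 patients, 93 per arm, for a 1-point LUSm difference with SD 2.96, alpha 5% and power 80%. That calculation concerns the two arms, not pass versus fail. The usual two-sided formula, 2 × (1.96 + 0.842)² × 2.96² / 1², gives 138 per arm and does not reproduce 93. This is a separate matter, and 186 is used here only as the planned total.

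Assumptions not in the documents:

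- SD 2.96, stated for LUSm, also applies to change scores.
- 5%, 10% or 18% of the 186 fail the SBT, giving 9, 19 or 33 failers. The 18% is the complement of the main protocol's 82% success rate, used only as a bound.
- The scan-condition shift c is 1 or 2 points.

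Formulas: SE = 2.96 × √(1/n_fail + 1/n_pass). P(significant) = 1 − Φ(1.96 − c/SE) + Φ(−1.96 − c/SE).

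Worked case, 19 versus 167 with c = 1: SE = 2.96 × √(0.0526 + 0.0060) = 0.717; c/SE = 1.395; P = 1 − Φ(0.565) + Φ(−3.355) = 0.287.

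| Failers / passers | c = 1 | c = 2 |
|---|---|---|
| 9 / 177 | 17% | 51% |
| 19 / 167 | 29% | 80% |
| 33 / 153 | 42% | 94% |

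A shift of zero gives the nominal 5%. The table shows how sensitive the test is to a shift; it does not estimate the shift in this trial.

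**The case against.** **Figure 7 may contain more.** The text lists only essential scans, which leaves room for others. The substudy promises LUSm at several times, sets separate objectives for PEEP during the SBT and aspiration at extubation, and schedules diaphragm and intercostal clips at the end of the SBT. An end-of-SBT LUSm is therefore plausible. This stands as a caveat. It does not remove the point, because no such scan is listed as essential and nothing ties ΔRCT for this outcome to one.

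**A failer scanned before reconnection is still in the condition that was failed.** This is correct, and the CRF identifies these patients. Reconnected failers are the harder case. Even so, no passer's second essential scan is in SBT mode.

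**The failure definition is already split.** The two-part definition allows extubation failure to be analysed among passers alone. The plan does not say that the ΔRCT correlation will be done that way.

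**Scope.** This is one of eleven mostly descriptive secondary outcomes in a nested substudy.

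**Stronger readings the documents do not support:**

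- A reader might infer that the contrast measures only scan condition. The documents show that the two effects are inseparable, not that one is absent.
- A reader might infer that passers must look worse. The main protocol's Introduction says lung volume may be recruited during the 1-hour rest, and prophylactic HFNC or NIV may act the same way. Suctioning applies to one arm only.
- A reader might extend the point to the between-arm comparison. Both arms follow the same scan scheme, and this argument does not challenge that contrast.

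**Conclusion.** The concern holds as one of attribution. Under the essential scans listed, the pass/fail test of ΔRCT cannot distinguish the effect of SBT failure from that of scan condition, and neither the CRF item nor blinded reading repairs this. The bias could act in either direction, and its size is unknown. The percentages above rest on an assumed shift, an assumed SBT failure rate and an LUSm standard deviation borrowed for change scores. The conclusion rests on the scan schedule and does not depend on them. It is conditional on figure 7 not making an end-of-SBT LUSm the basis of this outcome. The consequence is limited to this secondary outcome and to any ΔRCT correlation that counts SBT failers as extubation failures.

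**What to change.** In the substudy analysis wording:

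1. Do not test pass versus fail on these unlike scans. Report ΔRCT descriptively for passers (post-extubation) and, separately, for failers scanned in SBT mode and failers scanned after reconnection, using the item already in the CRF.
2. Analyse the correlation of ΔRCT with extubation failure among SBT passers only.
3. If figure 7 provides an LUSm at the end of the SBT, before reconnection or extubation, define ΔRCT for the pass/fail outcome from that scan only. Otherwise limit pass/fail testing of LUSm to the pre-SBT scan.
4. State the formula for ΔRCT and the pair of scans it uses.

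The cost is that one secondary significance test is dropped or rests on fewer patients. No new data collection is needed. Making an end-of-SBT LUSm essential for everyone would go further, but that changes image acquisition and not only analysis wording.
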